### **6.2.3 Intermediate Visits**

#### **TKA or THA Surgery**

- Give patients the pill bottle with the study drug or placebo pill.

#### **Visit 2 (standard of care post-operatively visit within 2 months of surgery)**

- Observe patient's recovery from TJA surgery as per standard of care
- Record participant's adherence to treatment program.
- Record patient standard sleepiness scale, PROMIS – Sleep Disturbance, VAS pain scores, collect sleep diary and opioid consumption.

### **6.2.4 Withdrawal/Early Termination Visit**

If a patient wishes to terminate early no further procedures or interventions will be performed and the patient will be allowed to continue their pre- or post-operative care as per standard of care

### **6.2.5 Unscheduled Visit**

Any unscheduled visits or contact from patients will be recorded in the EMR, which will be checked regularly by members of the research team for all study participants

### **6.2.6 Precautionary Medications, Treatments, and Procedures**

There is no precautionary medications, treatments, and or procedures associated with the use of Melatonin

### **6.3 Participant Access to Study Agent at Study Closure**

If a patient wishes to continue usage of melatonin after closure of the study they will be informed that it is a commercially available product they can obtain from any major retailer.

## **7 Assessment of Safety**

### **7.1 Specification of Safety Parameters**

All safety parameters including patients vital signs and clinical examination as per standard of care will be recorded in their EMR.

#### **7.1.1 Definition of Adverse Events (AE)**

An **adverse event** (AE) is any symptom, sign, illness or experience that develops or worsens in severity during the course of the study. Intercurrent illnesses or injuries should be regarded as adverse events. Abnormal results of diagnostic procedures are considered to be adverse events if the abnormality:

- results in study withdrawal
- is associated with a serious adverse event
- is associated with clinical signs or symptoms
- leads to additional treatment or to further diagnostic tests
- is considered by the investigator to be of clinical significance

### 7.1.2 Definition of Serious Adverse Events (SAE)

#### **Serious Adverse Event**

Adverse events are classified as serious or non-serious. A **serious adverse event** is any AE that is:

- fatal
- life-threatening
- requires or prolongs hospital stay
- results in persistent or significant disability or incapacity
- a congenital anomaly or birth defect
- an important medical event

Important medical events are those that may not be immediately life threatening, but are clearly of major clinical significance. They may jeopardize the subject, and may require intervention to prevent one of the other serious outcomes noted above. For example, drug overdose or abuse, a seizure that did not result in in-patient hospitalization, or intensive treatment of bronchospasm in an emergency department would typically be considered serious.

All adverse events that do not meet any of the criteria for serious should be regarded as **non-serious adverse events**.

### 7.1.3 Definition of Unanticipated Problems (UP)

#### **Unanticipated Problems Involving Risk to Subjects or Others**

Any incident, experience, or outcome that meets all of the following criteria:

- Unexpected in nature, severity, or frequency (i.e. not described in study-related documents such as the IRB-approved protocol or consent form, the investigators brochure, etc)
- Related or possibly related to participation in the research (i.e. possibly related means there is a reasonable possibility that the incident experience, or outcome may have been caused by the procedures involved in the research)
- Suggests that the research places subjects or others at greater risk of harm (including physical, psychological, economic, or social harm).

## 7.2 Classification of an Adverse Event

### 7.2.1 Severity of Event

For AEs not included in the protocol defined grading system, the following guidelines will be used to describe severity.

- **Mild** – Events require minimal or no treatment and do not interfere with the participant's daily activities.
- **Moderate** – Events result in a low level of inconvenience or concern with the therapeutic measures. Moderate events may cause some interference with functioning.
- **Severe** – Events interrupt a participant's usual daily activity and may require systemic drug therapy or other treatment. Severe events are usually potentially life-threatening or incapacitating.

### 7.2.2 Relationship to Study Agent

*The clinician's assessment of an AE's relationship to study agent (drug, biologic, device) is part of the documentation process, but it is not a factor in determining what is or is not reported in the study. If there is any doubt as to whether a clinical observation is an AE, the event should be reported. All AEs must*

*have their relationship to study agent assessed. In a clinical trial, the study product must always be suspect. To help assess, the following guidelines are used.*

- **Related** – *The AE is known to occur with the study agent, there is a reasonable possibility that the study agent caused the AE, or there is a temporal relationship between the study agent and event. Reasonable possibility means that there is evidence to suggest a causal relationship between the study agent and the AE.*
- **Not Related** – *There is not a reasonable possibility that the administration of the study agent caused the event, there is no temporal relationship between the study agent and event onset, or an alternate etiology has been established.*

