## **1.4 Potential Risks & Benefits**

### **1.4.1 Known Potential Risks**

Short term use of melatonin is safe, even in extreme doses with only mild adverse effects which can include dizziness, headache, nausea and sleepiness. Randomized clinical studies have indicated that even long-term exogenous melatonin only mild adverse effects such as dizziness and headaches comparable to placebo.

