### **8.4.3 Safety Analyses**

AE's will be recorded according to the Medical Dictionary for Regulatory Activities, counted once per individual occurrence, presented in terms of its severity and relationship to AE, and its start date, stop date, severity, relationship, outcome and duration will be reported. All AE's will be ascertained via PI report.

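### The Related and Not Related adverse-event definitions overlap with no precedence rule, and 8.4.3 plans no by-arm, per-patient safety summary

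*Combined protocol and SAP*

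**What the plan says.** Section 7.2.2 offers two classes for causality. Related applies if the effect is known for the agent, or "there is a reasonable possibility that the study agent caused the AE, or there is a temporal relationship between the study agent and event". Not Related applies if a reasonable possibility of causation is absent, or if "there is no temporal relationship between the study agent and event onset, or an alternate etiology has been established". Two further sentences guide the assessor: "Reasonable possibility means that there is evidence to suggest a causal relationship between the study agent and the AE", and "In a clinical trial, the study product must always be suspect". There is no intermediate class and no rule for an event that satisfies both lists.

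Section 8.5.1 starts dosing on postoperative day zero with 14 daily pills, so dosing coincides with early surgical recovery. Section 1.4.1 lists the agent's "mild adverse effects which can include dizziness, headache, nausea and sleepiness". Section 8.4.3 then states that events are "counted once per individual occurrence, presented in terms of its severity and relationship to AE", with dates, outcome and duration also reported. It does not mention treatment arm, number of patients affected, or a denominator.

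**The concern.** Both lists are joined by *or*, so each class can be entered through a single condition, and the conditions are not opposites of one another. Timing opens the first class. An established other cause opens the second. The two can hold together, and this trial makes that likely to matter: patients take the pill while recovering from surgery and anesthesia, and inpatient opioid use is itself a study measurement (6.1.1). Two qualified assessors could each follow 7.2.2 exactly and code the same event in opposite ways.

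The reported related/not-related split is what is at stake. Section 7.2.2 requires the assessment for every event, and 8.4.3 makes it one of the axes of presentation. A randomized comparison of all events would need no attribution, but 8.4.3 does not call for one. Counting by occurrence adds a second weakness, because counts of events do not show how many patients were affected.

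**Working it through.** The plan gives no figure on this point, so there is none to reproduce. The check is logical.

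**Inputs, all from 7.2.2.** K = effect known for the agent; P = reasonable possibility of causation; T = temporal relationship; A = alternate cause established. Each is yes or no, which gives 2 × 2 × 2 × 2 = 16 combinations.

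**Literal rules.**
- Related = K or P or T.
- Not Related = (not P) or (not T) or A.

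**All 16 combinations.**
- Related fails only if K, P and T are all no. A is free, so 2 combinations are Not Related only.
- Not Related fails only if P and T are yes and A is no. K is free, so 2 combinations are Related only.
- The other 16 − 2 − 2 = 12 meet both definitions. None meets neither.

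**Events with a temporal relationship (T = yes, 8 combinations).** All 8 are Related. Not Related fails only where P is yes and A is no (2 combinations), so 8 − 2 = 6 meet both.

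**Other ways to read Not Related.**

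| Reading of Not Related | Meet both, of 16 | Meet both with T = yes, of 8 |
|---|---|---|
| any one condition (literal) | 12 | 6 |
| (not P and not T) or A | 8 | 4 |
| all three conditions required | 1 | 0 |

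The last reading removes the overlap for events with T = yes, but all 8 are then Related and the variable no longer separates anything.

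**One case side by side.** A patient has nausea after an evening dose, and the assessor has established an opioid cause.
- It follows the dose and is a listed effect in 1.4.1, so K and T hold and it is Related.
- A holds, so it is Not Related.
- The sentence that keeps the product under suspicion does not cancel A, and the definition of reasonable possibility limits P but not T.

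**Is a substitute summary specified elsewhere?** Section 8.4.5 asks for baseline data by group within each joint cohort. Section 8.3 defines the intention-to-treat set for efficacy. Section 8.4.3 asks for neither a by-arm nor a per-patient display.

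**Precision of a by-arm summary.** Section 8.2 plans 64 patients per arm in each cohort, hence 64 + 64 = 128 per arm overall. The 95% half-width of a risk difference is widest when both risks are 50%: 1.96 × √(2 × 0.5 × 0.5 / n).
- n = 64: 1.96 × 0.0884 = 0.173.
- n = 128: 1.96 × 0.0625 = 0.1225.

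Randomization is not stratified by surgery type (8.5.1), so the arm sizes within each cohort are approximate.

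**The case against.** The case for leaving the text alone has real force.

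- **Relationship is only one attribute.** Section 7.2.2 says it does not decide what is reported, and 7.3 requires every event to be documented whatever its relationship. Severity, dates, outcome and duration do not depend on it. With 1:1 double-blind allocation (3.1), inconsistent coding should fall on both arms alike and add noise rather than bias. All of this stands. A reader might infer that the whole safety table is uninterpretable; the documents do not support that.
- **The second class needs a cause that has been established, not one that is merely plausible.** Section 7.3 reserves the judgment to people qualified to diagnose. This also stands: not every postoperative event falls in both classes. It does not help where another cause has in fact been established.
- **The suspicion sentence leans toward Related.** It does, but it is a stance and not a tie-break.
- **Unanticipated problems.** A reader might infer that the overlap also decides what reaches the IRB as an unanticipated problem, because 7.1.3 requires an event to be "Related or possibly related to participation in the research". That is not shown. Section 7.1.3 has its own reasonable-possibility test, has no timing or alternate-cause limb, and also requires the event to be unexpected. Sections 7.3.1 and 7.3.2 do not name relatedness as a condition for reporting adverse events or serious adverse events.
- **Repeated episodes.** A reader might infer that each night of a recurring symptom counts as a separate event. Section 7.3 can instead be read as treating an intermittent event as one event with its episodes recorded, so the size of any inflation is unknown.

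**Conclusion.** The concern holds for the attribution variable and for the missing summary, and no further. The two classes in 7.2.2 are not mutually exclusive, no rule resolves the overlap, and the related/not-related split is therefore unreliable. Under the literal reading, 6 of 8 combinations with a temporal relationship meet both definitions; under a softer reading, 4 of 8 do. These count logical cases with equal weight, some of them clinically unlikely. They say nothing about how often such events will occur.

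A reader might also infer that practically all events in the dosing window are Related by timing. That assumes onset during dosing counts as a temporal relationship, a term the protocol leaves undefined, and the documents give no event rates.

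Because all events are kept, all-cause results by arm can be recovered from the data. The gap is that 8.4.3 does not plan them and counts occurrences rather than patients. This should be corrected, but it is a defect of drafting and analysis specification; it does not invalidate the safety data.

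**What to change.** **In 7.2.2**, make the two classes mutually exclusive, or add one sentence saying which prevails when an event meets both. The sponsor should choose the rule consistently with its own stance that the product remains under suspicion. Making Not Related the default would reverse that stance and is not needed to cure the overlap.

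**In 8.4.3:**
- Correct the garbled phrase so that it refers to relationship to study agent.
- Make the main safety summary the number and proportion of patients with at least one adverse event by randomized arm, overall and within the THA and TKA cohorts, regardless of attribution.
- Give risk differences with 95% confidence intervals.
- Keep event counts and attribution as secondary listings.

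**Cost.** A sentence or two in 7.2.2, a paragraph in 8.4.3 and one extra table, with no new data collection. Intervals will be wide: a half-width of up to about 17 percentage points within a cohort and 12 overall. The table can be no better than the capture behind it. The schedule in 6.2 marks adverse-event collection only at Visit 2, and 8.4.3 relies on PI report, so the summary should be read with that in mind.

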### **7.2.3 Expectedness**

The principal investigator, [name] will be responsible for determining whether an AE is expected or unexpected. An AE will be considered unexpected if the nature, severity, or frequency of the event is not consistent with the risk information previously described for the study agent.

## **7.3 Time Period and Frequency for Event Assessment and Follow-Up**

The occurrence of an AE or SAE may come to the attention of study personnel during study visits and interviews of a study participant presenting for medical care, or upon review by a study monitor. All AEs including local and systemic reactions not meeting the criteria for SAEs will be captured on the appropriate RF. Information to be collected includes event description, time of onset, clinician's assessment of severity, relationship to study product (assessed only by those with the training and authority to make a diagnosis), and time of resolution/stabilization of the event. All AEs occurring while on study must be documented appropriately regardless of relationship. All AEs will be followed to adequate resolution.

Any medical condition that is present at the time that the participant is screened will be considered as baseline and not reported as an AE. However, if the study participant's condition deteriorates at any time during the study, it will be recorded as an AE. UPs will be recorded in the data collection system throughout the study.

Changes in the severity of an AE will be documented to allow an assessment of the duration of the event at each level of severity to be performed. AEs characterized as intermittent require documentation of onset and duration of each episode.

The PI will record all reportable events with start dates occurring any time after informed consent is obtained until 7 (for non-serious AEs) or 30 days (for SAEs) after the last day of study participation. At each study visit, the investigator will inquire about the occurrence of AE/SAEs since the last visit. Events will be followed for outcome information until resolution or stabilization.

All unresolved adverse events should be followed by the investigator until the events are resolved, the subject is lost to follow-up, or the adverse event is otherwise explained. At the last scheduled visit, the investigator should instruct each subject to report any subsequent event(s) that the subject, or the subject's personal physician, believes might reasonably be related to participation in this study.

### **7.3.1 Adverse Event Reporting**

Any AE's encountered during the study will be identified by research personnel and brought to the attention of the PI. After investigation by the PI of the surrounding circumstances they will then be reported as quickly as possible, within 1 week, to the IRB, as indicated

### **7.3.2 Serious Adverse Event Reporting**

Any SAE's encountered during the study will be identified by research personnel and brought to the immediate attention of the PI. They will then be reported as quickly as possible, within 3 days, to the IRB

### **7.3.3 Unanticipated Problem Reporting**

Incidents or events that meet the OHRP criteria for UPs require the creation and completion of an UP report form. It is the site investigator's responsibility to report UPs to their IRB. The UP report will include the following information:

- Protocol identifying information: protocol title and number, PI's name, and the IRB project number;
- A detailed description of the event, incident, experience, or outcome;
- An explanation of the basis for determining that the event, incident, experience, or outcome represents an UP;
- A description of any changes to the protocol or other corrective actions that have been taken or are proposed in response to the UP.

To satisfy the requirement for prompt reporting, UPs will be reported using the following timeline:

- UPs that are SAEs will be reported to the IRB and to [name]/lead PI within 1 week of the investigator becoming aware of the event.
- Any other UP will be reported to the IRB and to [name]/lead PI within 1 week of the investigator becoming aware of the problem.
- All UPs should be reported to appropriate institutional officials (as required by an institution's written reporting procedures), the supporting agency head (or designee), and OHRP within 1 week of the IR's receipt of the report of the problem from the investigator.

### **7.3.4 Reporting of Pregnancy**

No pregnant patients will be included in the study. Any patient who becomes pregnant during the study will be removed from the study group.

## **7.4 Reporting Procedures – Notifying [name]**

The study clinician will complete a SAE Form within the following timelines:

- All deaths and immediately life-threatening events, whether related or unrelated, will be recorded on the SAE Form and submitted to [name] within 24 hours of site awareness. See Section 1, Key Roles for contact information.
- Other SAEs regardless of relationship will be submitted to [name] within 72 hours of site awareness.

All SAEs will be followed until satisfactory resolution or until the site investigator deems the event to be chronic or the adherence to be stable. Other supporting documentation of the event may be requested by [name] and should be provided as soon as possible.

As a follow-up to the initial report, within the following 48 hours of awareness of the event, the investigator shall provide further information, as applicable, on the unanticipated event or the unanticipated problem in the form of a written narrative. This should include a copy of the completed Unanticipated Problem form, and any other diagnostic information that will assist the understanding of the event.

## **7.5 Safety Oversight**

It is the responsibility of the Principal Investigator to oversee the safety of the study. This safety monitoring will include careful assessment and appropriate reporting of adverse events as noted above. Medical monitoring will include a regular assessment of the number and type of serious adverse events. PI will oversee data on an annual basis by creating reports from data entered into RedCap.

# **8 Clinical Monitoring**

Clinical site monitoring is conducted to ensure that the rights and well-being of human subjects are protected, that the reported trial data are accurate, complete, and verifiable, and that the conduct of the trial is in compliance with the currently approved protocol/amendment(s), with GCP, and with applicable regulatory requirement(s).

- Monitoring for this study will be performed by the PI.
- Monitoring will be on sight with frequent random checks of data. At conclusion of the study another independent member of the LOH arthroplasty research team not affiliated with the study will check all available data to ensure its validity

# **Statistical Considerations**

## **8.1 Statistical Hypotheses**

- Primary endpoint: The null hypothesis is that there is no difference between the melatonin and placebo group in the mean ESS score from days 1-14 postoperatively. The alternative hypothesis is that there is a difference between the melatonin and placebo group in the mean ESS score during any of these time points
- Secondary endpoints:
  - Hours of sleeping measured each day from days 1-14 for overnight sleep: The null hypothesis is that there is no difference between the melatonin and placebo group in the mean hours of sleeping at these time points. The alternative hypothesis is that there is a difference between the melatonin and placebo group in the mean hours of sleeping at these time points. Nighttime awakenings are those that require an additional dose of pain medication to go back to sleep.
  - Other secondary endpoints to be listed

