## 1 Introduction, Background Information and Scientific Rationale

### 1.1 *Background Information and Relevant Literature*

Utilization of total hip and knee arthroplasty (THA and TKA, respectively) has increased over the last decade and is expected to continue to rise as the population of the United States ages. By 2030, over 2 million total joint arthroplasty (TJA) procedures are anticipated to be performed annually. With increasing numbers and to maintain excellent patient outcomes after total joint arthroplasty, it has become important to optimize every aspect of patient recovery. Sleep disturbance is a routinely encountered problem during the perioperative period in adults undergoing elective surgery. Sleep in postoperative patients is negatively influenced by exposure to anesthesia and the presence of postoperative pain. Reciprocally, poor sleep also portends poor coping and exacerbation of post-operative pain. Nighttime awakenings may be frequent, and require the use of additional pain medication to go back to sleep.

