### 1.3 *Rationale*

Sleep disruption following elective, primary total joint arthroplasty is very common. The cause is likely multifactorial, resulting from anxiety, anesthesia, the patient's recovery environment, and pain. Overall tiredness can lead to decreased energy, restlessness, less ambulation, and slow progress with physical therapy and recovery. Melatonin is an inexpensive, over the counter dietary supplement with an established safety profile that has been used to help create a more restful sleep cycle. There is no consensus as to the utility, dose, duration, or timing of melatonin administration in the period before and after elective hip and knee arthroplasty to improve sleep quality. This study design is supported by sleep disturbance usually occurs within the first 2 weeks of surgery due to a disrupted sleep wake cycle and pain. 5mg is a safe and effective starting dose for any sleep disturbance. Further, inconsistent methods of assessing patients' sleep and pain postoperatively has made the study of sleep quality difficult.

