## **2 Objectives and Purpose**

### **2.1 Primary Objective**

The primary objective is the Epworth Sleep Score used to evaluate the impact of melatonin use on the quality of sleep, including total hours of sleep and nighttime awakenings in patients undergoing elective primary total hip and knee arthroplasty.

Secondary Objectives are to monitor and investigate hospital length of stay, and narcotic consumption patterns, scores in patients who take melatonin as a sleep aid for 14 days after surgery.

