### **3.2 Study Endpoints**

#### **3.2.1 Primary Study Endpoints**

The primary endpoint will be the Epworth Sleep Score for patients indicating the impact of melatonin on quality of sleep, including total hours of sleep and nighttime awakening. The ESS will be evaluated post-operatively from days 1-14.

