### **8.4.2 Analysis of the Secondary Efficacy Endpoints**

The secondary endpoints include number of total hours of sleep, number of nighttime awakenings, and narcotic consumption.

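### The nighttime-awakenings endpoint counts only awakenings treated with a pain-medication dose, so this secondary sleep measure mixes waking with analgesic use

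*Combined protocol and SAP*

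**What the plan says.** Section 8.1 (Statistical Hypotheses) gives the only definition in the documents, at the end of the bullet on hours of sleep: "Nighttime awakenings are those that require an additional dose of pain medication to go back to sleep". No separate hypothesis is stated for awakenings.

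Elsewhere the term carries no analgesic condition:

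- Section 2.1 names it as part of "quality of sleep, including total hours of sleep and nighttime awakenings in patients undergoing elective primary total hip and knee arthroplasty".
- Section 3.2.1 describes the primary endpoint as indicating the "impact of melatonin on quality of sleep, including total hours of sleep and nighttime awakening".
- Section 8.4.2 lists the secondary endpoints as "number of total hours of sleep, number of nighttime awakenings, and narcotic consumption". It gives no analysis method for any of them.

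Two background statements bear on the definition. Section 1.1 says: "Nighttime awakenings may be frequent, and require the use of additional pain medication to go back to sleep". Section 1.3 says of sleep disruption: "The cause is likely multifactorial, resulting from anxiety, anesthesia, the patient's recovery environment, and pain".

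Section 6.1.1 provides for a daily sleep diary over the first two weeks but does not describe its items.

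**The concern.** The objective concerns sleep, but the counting rule needs two events: the patient wakes, and the patient needs another dose to get back to sleep. A patient who wakes five times from noise or anxiety and takes nothing scores zero. A patient who wakes once and takes a dose scores one. The count therefore depends on pain, on access to medication and on willingness to take it, as well as on sleep.

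Two misreadings become possible. A real reduction in undosed awakenings would not appear in this count. Conversely, a reduction in overnight dosing with no change in waking would be reported as fewer awakenings. The second is not far-fetched, because Section 1.2.2 itself cites analgesic effects of perioperative melatonin.

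**Working it through.** **The plan's own figure.** Section 8.2 gives an ESS difference of 2.65, SD 5.3, two-sided alpha 0.05 and 80% power. The normal approximation is n = 2 × (1.960 + 0.842)² × (5.3 / 2.65)² = 2 × 7.85 × 4 = 62.8, so 63 per arm. The t-test version gives 63.77, so 64 per arm and 128 per cohort, as stated. Nothing in this depends on how awakenings are defined.

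**What must be assumed.** The documents give no awakening rate, between-patient variance, treatment effect on awakenings, or share q of awakenings that lead to a dose. The share left out of the count is 1 − q: 50%, 75%, 90% or 95% for q = 0.50, 0.25, 0.10 or 0.05. Everything below is illustration for one cohort with 64 per arm.

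**Case A: melatonin reduces dosed and undosed awakenings alike.** Assumptions: 2 awakenings per night on placebo, rate ratio 0.6, gamma-Poisson counts totalled over 14 nights, between-patient variance 0.5, rank-sum test, 2,000 simulated trials per setting. Two runs are shown where available, to indicate simulation error.

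| Dosed share q | Counted per night | Power | Loss in points |
|---|---|---|---|
| All counted | 2 | 0.937, 0.947 | – |
| 0.50 | 1 | 0.927 (one run, against 0.947) | 2.0 |
| 0.25 | 0.5 | 0.884, 0.886 | 5.3, 6.1 |
| 0.10 | 0.2 | 0.763, 0.764 | 17.4, 18.3 |
| 0.05 | 0.1 | 0.603, 0.599 | 33.4, 34.8 |

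The level is sensitive to the assumed variance: at 1.0 instead of 0.5, power with all awakenings counted is only about 0.66.

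A smaller effect can be checked by hand. Take rate ratio 0.8, variance 0.3, μ₀ = 2 × q × 14 and μ₁ = 0.8 × μ₀. Then v = [(1/μ₀ + 0.3) + (1/μ₁ + 0.3)] / 64, and power = Φ(|ln 0.8| / √v − 1.96).

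- All counted: μ₀ = 28, μ₁ = 22.4, v = (0.336 + 0.345) / 64 = 0.0106, power = Φ(0.223 / 0.103 − 1.96) = 0.58.
- q = 0.10: μ₀ = 2.8, μ₁ = 2.24, v = (0.657 + 0.746) / 64 = 0.0219, power = Φ(0.223 / 0.148 − 1.96) = 0.33.
- By the same formula, power is 0.54 at q = 0.50 and 0.46 at q = 0.25.

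**Case B: melatonin reduces only undosed awakenings.** With a 40% cut in these, the rate ratio for all awakenings is q + (1 − q) × 0.6, which is 0.64 at q = 0.10 and 0.70 at q = 0.25. Under the Case A model, power on all awakenings is about 0.88 and 0.70. For the endpoint as defined, the rate ratio is 1.00, and it rejects only at about the 5% false-positive rate. A larger sample would not help, because the effect is absent from what is counted.

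**The case against.** The definition may be deliberate. Section 1.1 ties awakenings to extra pain medication, and counting only awakenings that need treatment is a recognizable restricted endpoint. That is fair, and it is a reason to keep the restricted count under its own name. It does not justify using that count as the general measure of awakenings that Sections 2.1, 3.2.1 and 8.4.2 describe: Section 1.1 is background, and Section 1.3 expects causes other than pain.

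A reader might infer that undosed awakenings are lost and that the trial cannot answer its question about waking. The documents do not show this. The diary's items are not described, so it may record every awakening. Undosed awakenings could also show in total hours of sleep and in PROMIS Sleep Disturbance (Sections 6.2.2 and 6.2.3). They are left out only of the count as defined.

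A reader might also call this purely an analgesia endpoint that duplicates narcotic consumption. That goes too far, since waking is still required. Section 6.1.1 takes opioid use from inpatient records, and the definition says pain medication rather than opioid, so on that basis the overlap is confined to inpatient opioid doses. The Protocol Summary lists daily narcotic consumption for 14 days, which would widen the overlap if it governs.

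Finally, the large power losses arise only if 90% to 95% of awakenings are undosed. Nothing in the documents supports that share, or any other.

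**Conclusion.** The point stands for a secondary endpoint. No section broadens the definition in Section 8.1, and it does not match the use of the term elsewhere in the plan. Followed as written, the endpoint omits undosed awakenings and cannot separate a change in waking from a change in dosing.

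The loss of power is not established at any one value. Under the Case A assumptions it runs from about 2 points with half of awakenings dosed to 33 to 35 points with 5% dosed. The firmer consequence is one of interpretation: an effect confined to undosed awakenings would show as no effect, whatever the sample size.

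It would be wrong to infer that the primary result is at risk. Sections 2.1 and 3.2.1 mention awakenings in describing what the ESS is meant to reflect, but the tested primary hypothesis (Section 8.1), its analysis (Section 8.4.1) and the 64 per arm (Section 8.2) rest on the ESS alone. The plan states no power for awakenings. This is a cheap improvement to a secondary measure.

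**What to change.** In Section 8.1, define the secondary endpoint as all nighttime awakenings per night, taken from the daily sleep diary. Have the diary flag each awakening that is followed by a pain-medication dose, and report that subset as a separately labelled secondary measure. Use the same terms in Sections 2.1, 3.2.1, 8.1 and 8.4.2. Settle the diary items before they are used: if the diary follows the present definition, undosed awakenings may not be recoverable later.

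The cost is slightly more recording by patients and one more secondary measure to report. The exact change to the form depends on a diary layout that the documents do not show. The sample size does not change, and the proposal concerns measurement only, not how pain is treated.
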